9.2 Internal Pilot

An internal pilot will run from months 7-16 of the grant timeline and use a traffic light system to assess key progression criteria regarding site opening, recruitment, and adherence to the study protocol (25). The internal pilot will follow the same processes as the main trial; participants enrolled in the pilot will be included in the analysis of the main trial.

We will use a traffic light system to assess progression from internal pilot stage to the full trial as below:

	Red	Amber	Green
Number of sites opened	<14	14-18	≥19
Patient recruitment relative to target	<85%	≥85 and <100%	≥100%
Non-adherence	>15%	>5% and ≤15%	≤5%

Non-adherence is defined as the percentage of all randomised patients who meet either of the following criteria:

- Randomised to no routine GRV measurement and have had one or more GRV measurements taken within the first three calendar days following randomisation (except for any measurement taken in response to a recorded clinical indication)
- Randomised to routine GRV measurement and no measurement has been taken in at least one whole calendar day spent in PICU following randomisation, up to and including the third day after randomisation

If all the green criteria are met, the trial will progress from the internal pilot to the full trial unchanged. If any of the amber criteria are met, we will consult the Trial Steering Committee (TSC) and we will act upon their advice to address the issues raised. If any of the red criteria are met, we will discuss urgently with the TSC and the funder and consider remedial actions, including discontinuation. An internal pilot report will be reviewed by the TSC, and any required remedial plans developed before a pilot phase report is submitted to the NIHR HTA.

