12.2 Comparator

The comparator (control arm) is routine (at least 6 hourly) GRV measurements to guide enteral feeding.

Patients should be monitored for feed intolerance using the GRV measurements as well as vomiting, and other gastrointestinal or systemic signs. The frequency of GRV should be as per standard local practice but should be at least 6 hourly. Further guidance can be found in Appendix 1 (Example Feeding Guidelines).

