12.6 End of Treatment

For both groups, trial treatment will continue until tube feeds have been discontinued during the PICU admission or until discharge from PICU, whichever is sooner. The trial treatment will apply at any point the patient requires tube feeds during their PICU admission (for example, the patient will return to their assigned treatment group in the case of failed attempt to stop tube feeding). The decision to discontinue tube feeds is at the discretion of the clinical team.

13. Trial Procedures

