16.3 Clinical effectiveness analysis methods

16.3.1 General principles

All analyses will be outlined in a statistical analysis plan (SAP) approved by an independent trial steering committee and seen by the independent data monitoring committee.

The following analysis populations will be defined:

- Per protocol (PP), which will exclude patients where consent to data collection has been withheld or withdrawn before day 30, and also patients classed as non-compliant as defined previously for the pilot evaluation stage.
- Intention to treat (ITT), which excludes patients where consent to data collection has been withheld or withdrawn for all data processing.
- ITT (energy intake), which excludes patients where consent to data collection has been withheld before 72 hours or withdrawn for all data processing.

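### The control-arm non-adherence rule ignores the end of tube feeding, so the per-protocol set drops correctly treated control children while matching intervention children stay in

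*Protocol*

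**What the plan says.** Section 9.2 of the protocol defines non-adherence separately for each arm. A control child is non-adherent if "no measurement has been taken in at least one whole calendar day spent in PICU following randomisation". The window closes on day 3, and the only condition is presence in PICU for the whole day. An intervention child is non-adherent only if found to "have had one or more GRV measurements taken within the first three calendar days following randomisation", and measurements made for a recorded clinical indication are exempt.

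Section 12.6 sets the period over which the allocation applies: "trial treatment will continue until tube feeds have been discontinued during the PICU admission or until discharge from PICU, whichever is sooner". It adds: "The trial treatment will apply at any point the patient requires tube feeds during their PICU admission".

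Section 16.3.1 removes from the PP set "patients classed as non-compliant as defined previously for the pilot evaluation stage". Section 16.3.2 declares non-inferiority on the ventilator-free-days composite only if the upper confidence limit for the odds ratio is no more than 1.2 in both PP and ITT.

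**The concern.** Take two children whose tube feeds are discontinued on the day after randomisation and who then spend one further whole calendar day in PICU with no gastric residual volume (GRV) taken. Under section 12.6 trial treatment has ended for both, and neither has departed from the protocol. Under section 9.2 the control child is non-adherent and leaves the PP set, while the intervention child is adherent and stays.

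The exclusion therefore acts in one arm only, and it is triggered by feeding status after randomisation. That status is plausibly related to the outcome: a child whose tube feeds end within three days has often recovered early, and some may have deteriorated. The PP comparison then carries a selection effect that has nothing to do with adherence, in an analysis that must be passed before non-inferiority can be declared. The same children also inflate the non-adherence percentage in the pilot progression table.

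**Working it through.** **1. Text.** Section 9.2 requires a measurement on every whole PICU day to day 3. Section 12.6 ties trial treatment to tube feeding. The two disagree on days after tube feeds have been discontinued, and section 16.3.1 imports the section 9.2 rule unchanged.

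**2. Planning distribution (section 16.1).** Mortality is 4.2%; ventilation duration is log-normal with median 2.9 days and lower quartile 1.0 day.
- σ = ln(2.9/1.0)/0.6745 = 1.579.
- P(duration ≤ 2 days) = Φ((ln 2 − ln 2.9)/1.579) = 0.407. Multiplied by the 95.8% who survive, this puts 39.0% of children in the two best categories.
- With durations cut into whole days and death as the worst category, Σp³ = 0.0191.

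**3. Reproducing the stated size.** The Whitehead formula with 1:1 allocation gives N = 12(1.960 + 1.282)² / [(ln 1.2)² × (1 − 0.0191)] = 3,867. Other ways of cutting days give 3,836 to 3,939, against the stated 4,000. Inflation gives 4,000/0.85 = 4,706 or 4,000/(0.90 × 0.95) = 4,678, against the stated 4,700. The sample size is not in dispute.

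**4. Precision.** At 4,000 evaluable, SE(ln OR) = √(12/(4,000 × 0.9809)) = 0.0553. Power at a true OR of 1.00 is Φ(0.1823/0.0553 − 1.96) = 91%.

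**5. Effect of one-arm losses.** The documents do not give the share of control children affected, so it is assumed and varied. The stated share is removed from the control distribution, the remainder is rescaled, and a proportional odds model is fitted to the expected proportions. The chance that PP meets the margin is Φ((ln 1.2 − ln OR_PP)/0.0553 − 1.96). For example, with OR_PP = 1.09 (1.0897 unrounded): (0.1823 − 0.0859)/0.0553 − 1.96 = −0.22, giving 41%.

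| Controls removed | From those ventilated ≤ 2 days, true OR 1.20: PP OR | PP alone meets margin | From the sickest third, true OR 1.00: PP OR | PP power |
|---|---|---|---|---|
| 0% | 1.20 | 2.5% | 1.00 | 91% |
| 1% | 1.18 | 5% | 1.02 | 83–84% |
| 2.5% | 1.145 | 13% | 1.05 | 64–66% |
| 5% | 1.09 | 41% | 1.11 | 26–29% |

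The ranges in the last column reflect small differences in how the sickest third is cut. Removing 5% of controls from the ≤ 2-day group means losing 0.05/0.390 = 13% of that group.

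**6. Mixed losses.** Removing 2.5% of controls from each end gives a PP OR of about 1.004 at a true OR of 1.00. PP power is then 89.5%, and the chance of meeting the margin at a true OR of 1.20 is 1.9%. The two directions nearly cancel.

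**7. Pilot.** With 1:1 allocation, 5% of controls is 2.5% of all randomised children. Taken alone, that sits inside the green band of at most 5%, so the progression table would not reveal the problem.

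**The case against.** **ITT must also pass.** This stands and limits the harm. A reader might take the 41% as the trial's false-positive rate. It is not. At a true OR of 1.20, ITT meets the margin 2.5% of the time whatever happens in PP, so favourable PP bias cannot lift the overall rate above that. The objection does not help in the other direction: if PP fails because of this rule, non-inferiority cannot be declared whatever ITT shows.

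**Few children will be caught.** This probably stands. Entry requires that no extubation is planned within 48 hours, the window is three days, a whole further PICU day must pass, tube feeding can continue after extubation, and children who leave PICU accrue no further days. The entry criterion may also make the 39% in the two best categories too high for this population. The 5% row is an upper illustration, not an estimate.

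**The direction is unknown.** This stands. Step 6 shows that balanced losses do little damage, so it would be too strong to say that PP cannot do its job. What can be said is that its bias depends on a balance nobody has measured.

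**A child held nil by mouth.** A reader might extend the point to any day without feed. The documents do not support that clearly. Section 12.6 speaks of feeds being discontinued, not paused, and the example guideline in Appendix 1 has GRV reassessed while feeds are withheld. The unfavourable column of the table leans partly on such children and is correspondingly less secure.

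**One measurement a day against the comparator schedule.** Section 12.2 says: "The frequency of GRV should be as per standard local practice but should be at least 6 hourly". A reader might infer that the PP threshold must match this. How strict a PP definition should be is a design choice, and a stricter one could exclude more controls and enlarge the one-arm selection.

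**The analysis plan may settle it.** It might, but the protocol states the rule in full and expressly reuses it for PP. This is a fixed definition that conflicts with section 12.6, not a detail left open.

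**Conclusion.** The rule is wrong as written. Sections 9.2 and 16.3.1 conflict with section 12.6, and the effect is to drop from PP, in the control arm only, children who were treated as planned.

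The size cannot be fixed from the documents. Under the planning distribution, each 1% of controls lost from the short-ventilation group moves the PP odds ratio by about 0.02 towards non-inferiority; losses from the sickest third move it by a similar amount the other way. The consequences are a weaker second check in the first case and a possible block on a true non-inferiority finding in the second. The figures assume that all losses come from one end of the distribution and that 4,000 children remain evaluable.

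The pilot effect is an overstatement of non-adherence. A reader might infer that it could stop the trial, but an amber or red result leads to discussion with the steering committee (and, for red, the funder), not to automatic stopping.

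**What to change.** Reconcile sections 9.2 and 16.3.1 with section 12.6. Count a control-arm day without a GRV as non-adherence only if trial treatment still applied that day, meaning that tube feeding had not been discontinued and the child was in PICU for the whole day. State explicitly how a day with feeds paused is classified.

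Leave the intervention-arm criterion unchanged. Restricting it to fully tube-fed days would miss routine measurements taken on part-fed days. Keep the once-a-day threshold. Use the same wording for the pilot criterion and the PP set, and fix it before any unblinded analysis.

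The cost is one reworded definition and a check of each control child's feeding status on each day to day 3. Section 13.1 already schedules enteral feeding data at days 3 and 7, though it does not show the level of daily detail. Measured control-arm non-adherence may change slightly.

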9.3 Trial Setting

NHS Paediatric Intensive Care units (PICUs) in the UK.

9.4 Site Requirements

- Active participation in the Paediatric Intensive Care Audit Network for the UK and Ireland (PICANet) or be able to collect detailed data on patient interventions and outcomes
- Compliance with all responsibilities as stated in the GASTRIC-PICU Site Agreement

- Compliance with the study treatments, follow-up schedules and all requirements of the study protocol
- Compliance with the Research Governance Framework or Policy Framework for Health and Social Care Research and International Conference on Harmonisation guidelines on Good Clinical Practice (ICH-GCP).

9.5 Site Responsibilities

- Identify a Principal Investigator (PI) or two co-PIs to lead the GASTRIC-PICU trial.
- If possible, appoint an Associate/Sub-PI to assist with the running of the trial.
- Identify a Research Nurse (or equivalent) responsible for day-to-day local trial coordination.
- Identify doctor/nurse/dietitian champions for the GASTRIC-PICU trial in the unit.
- Agree to incorporate the GASTRIC-PICU trial into routine critical care clinical practice, including GRV monitoring/measurement, highlighting the importance of systematic screening for potential eligible patients and prompt randomisation.
- Agree to adhere to participants randomised allocation and adhere to the trial protocol.
- Agree to aim to randomise all eligible patients and to maintain a Screening Log.
- Agree to data collection requirements.
- Check survival status at 6 months prior to follow up questionnaire/s.

9.6 Site Initiation and Activation

ICNARC Clinical Trials Unit (CTU) will ensure that the necessary documentation is in place before activating each site.

The following documentation must be in place prior to a site being activated for recruitment:

- A completed site initiation visit with adequate attendance to ensure knowledge of GASTRIC-PICU can be disseminated throughout the unit.
- All relevant institutional approvals (e.g., confirmation of capacity and capability).
- A fully signed GASTRIC-PICU Site Agreement.
- An up-to-date Delegation Log and Training Log.

Once activated, the site may start to screen for eligible patients. Once the site has been activated, the PI is responsible for ensuring:

- Adherence with the most recent approved version of the trial protocol.
- Training of relevant site staff in accordance with the trial protocol and Good Clinical Practice (GCP) requirements.
- Appropriate means to identify and randomise eligible patients into the trial.
- Timely data collection, entry and validation.
- Prompt notification of all serious adverse events (SAEs).

All local staff (i.e., PIs, local investigators, research teams) involved in the conduct of the trial must be listed and signed off on the Delegation Log, once trained, to carry out their delegated duties. The Delegation Log should be copied and sent to the GASTRIC-PICU Team at the ICNARC CTU whenever changes are made.

Staff members solely involved in the screening and randomisation of patients should be provided with trial-specific training to carry out these tasks and recorded on the Training Log (full GCP training will not be required for these staff members).

10. Participant Eligibility Criteria

To be eligible for the GASTRIC-PICU trial, patients must meet all the inclusion criteria and none of the exclusion criteria **at the point of randomisation**. Patients must be enrolled within 24 hours of first meeting the eligibility criteria.

10.1 Inclusion Criteria

- Aged ≥ 37 weeks corrected gestational age and < 16 years at the time of randomisation
- Receiving invasive mechanical ventilation (with extubation not planned in the next 48 hours)
- Intention to start feeding via the gastric route (including gastrostomy)

10.2 Exclusion Criteria

- Post pyloric feeding or jejunostomy
- End-of-life care plan in place with limitation of resuscitation
- Children on long term mechanical ventilation
- Current or recent gut pathology or surgery (e.g., necrotising enterocolitis (NEC), active GI bleeding, or any intestinal surgery)
- Known to have been enrolled in the GASTRIC-PICU trial in the last 6 months

10.3 Co-Enrolment

Co-enrolment will be permitted with observational studies (including those collecting samples) without prior agreement needed.

The GASTRIC-PICU trial investigators will consider co-enrolment of participants onto other interventional studies where there is no possible conflict with the GASTRIC-PICU trial objectives. We will follow previous experience and existing guidelines from the Paediatric Critical Care Society (PCCS) regarding co-enrolment to other clinical trials to maximise patient involvement in research. Co-enrolment agreements will be put in place on a trial-by-trial basis.

11. Trial Procedures

11.1 Screening

Potentially eligible patients admitted (or accepted for admission) to the participating PICU will be screened against the inclusion/exclusion criteria by the local clinical team, supported by the site research team. Screening Logs will record the reason patients are eligible but are subsequently not enrolled.

11.2 Randomisation

Randomisation must occur as soon as eligibility has been confirmed and will be carried out by the trained site staff. Patients will be randomised on a 1:1 basis to either 'No routine measurement of gastric residual

volume' or 'Routine at least 6 hourly measurement of gastric residual volume' using a central web-based randomisation service. Allocation will be stratified by site, age on admission (<1 month, \geq 1 month to <12 months, \geq 12 months) and main reason for admission (cardiac vs other). The service will be available 24 hours a day, seven days a week.

The staff member who randomised the patient is responsible for informing the clinical team responsible for the patients care of the randomisation. Site teams are responsible for establishing robust procedures to ensure this information is not missed. The local site research team will be notified of the enrolment by email. Following randomisation, each participant will be assigned a unique GASTRIC-PICU trial number and the CRF should be completed by the local site research team.

11.3 Consent Procedures

Children who are eligible for GASTRIC-PICU trial will often become so during a period of life-threatening illness. This is a profoundly stressful situation for parents/guardians during which time there are ethical concerns both about the burden placed of trying to understand the trial and their ability to provide informed consent during a time of great distress. Furthermore, as starting feeds occurs within the first 6-12 hours of admission and delay in commencing feeds would not be normal care, we will start feeds once the child is randomised.

GASTRIC-PICU trial will use a deferred consent model ('research without prior consent'). Once a patient is identified as being eligible for the study (i.e., satisfies inclusion and exclusion criteria), they will be randomised and the randomly assigned treatment will be commenced as soon as possible.

This model, developed in line with the CONseNt methods in paediatric Emergency and urgent Care Trials (CONNECT) study guidance (16) has been found to be acceptable to parents/guardians, as well as to clinicians, in several recent RCTs conducted in the paediatric critical care setting (8, 27-29). Findings from these studies have been incorporated into our consent procedures and will be used for training at sites.

11.3.1 Consent Prior to Hospital Discharge

Once notified of the randomisation of a patient to the study, a delegated member of the site research team will approach the parents/legal guardian to discuss the study as soon as practical and appropriate. This will usually be within 24-48 hours of randomisation, however, this will depend on the patient's condition and will be left to the discretion of the clinical team. If the patient has died or been discharged prior to their parents/legal guardians being approached, then the parents/legal guardians will be approached at a later point (please, see section 11.3.2 and 11.3.3).

Before approaching the parent/legal guardian, the research team member will discuss with the clinical staff that the patient is stable and that the timing is appropriate. If the patient's condition has not stabilised or the clinical team feel it is not an appropriate time, additional time should be allowed before approaching the parent/legal guardian. These discussions should be recorded in the patients' clinical notes.

Once approached, a Participant Information Sheet (PIS) for parents/legal guardians will be provided. The PIS will identify the title of the study and the Chief Investigator (CI) and include information about the purpose of the study, the implications of participating or not, participant confidentiality, use of personal data, data security, and the future availability of the results of the study. In addition to the PIS, and as advised by the Children and Young People's group (CYAG), parents/legal guardians will have the option to receive additional information, explaining the trial and its procedures, available on a video and accessed via scanning a QR code on the PIS.

A consent form will be provided indicating that: the information given, orally and in writing, has been read and understood, participation is voluntary and can be withdrawn at any time without consequence, and that consent is given for access to medical records for data collection. Parents/legal guardians will be given time

to read the PIS and have an opportunity to ask any questions they may have about their child's participation in the GASTRIC-PICU trial.

After the person seeking consent has checked that the PIS and Consent Form are understood, they will invite the parent/legal guardian to sign the Consent Form and will then add their own name and countersign. A copy will be given to the parent/legal guardian, a copy placed in the child's medical notes and the original kept in the Investigator Site File.

Due to age and the severity of illness and its impact on the mental state of the target population, it will not be possible to involve study participants in the consenting process. Instead, assent will be obtained from children 8 years-old and over prior to hospital discharge if their condition allows. Study participants will be provided with an age-appropriate PIS and asked to sign an Assent Form, if appropriate. Parents/legal guardians will be involved in this discussion. If the participant is likely to regain capacity following hospital discharge, then an age-appropriate PIS will be provided to parents/legal representatives to discuss with the participant following recovery.

If the participant is transferred to another hospital participating in the GASTRIC-PICU trial before the consent procedures are complete, then the originating research team will hand-over to the receiving hospital. If a participant is transferred to a non-participating site, the consent procedure in section 11.3.2 should be followed.

11.3.2 Discharge Prior to Consent Being Sought

In the event where a participant is discharged from hospital before consent has been sought or confirmed, the most appropriate member of the site research team will attempt at least one phone call to the parents/legal guardians within five working days of hospital discharge to inform them of the participant's involvement in the study and provide more details. Following on from the call, as well as if there is no response to the call, the parents/legal guardians will be sent the covering letter for discharged patients and a copy of the PIS by post. Where possible, the letter should be signed by a clinical team member who is known to the family. The letter will explain that the participant has already been included in the study and how to opt-out. It will direct them to the information sheet for detailed information on the study and provide telephone contact details if parents/legal guardians wish to discuss the study with a member of the site research team.

The letter will not be sent if the parents/legal guardians will opt out from the trial on the call with the site team.

If no objection is received within four weeks of receipt of the letter, then the participant's data will be included in the study.

For this group of participants, the use of their confidential patient information (required for data linkage to NHS Digital and PICANet) will be conducted under the provisions of Section 251 of the National Health Service Act 2006 (subject to approval from the Confidentiality Advisory Group). The justification for requesting Section 251 support is to eliminate the risk of bias from excluding information from specific subsets of the patients enrolled in the study.

